### **6.1.2 Pharmacokinetic studies**

**Plasma Sirolimus:** Levels will be determined by commercially available assay. Sirolimus levels will be obtained **just prior** to the dosing on Day 4

## 7 Statistical Plan

### 7.1 Sample Size and Study Duration

This study is considered a phase II study.

For the MDS Arm A:

The optimal two-stage design to test the null hypothesis that  $P \leq 0.230$  versus the alternative that  $P \geq 0.400$  has an expected sample size of 24.60 and a probability of early termination of 0.592. If the drug is actually not effective, there is a 0.090 probability of concluding that it is (the target for this value was 0.100). If the drug is actually effective, there is a 0.200 probability of concluding that it is not (the target for this value was 0.200). After testing the drug on 14 patients in the first stage, the trial will be terminated if 3 or fewer respond. If the trial goes on to the second stage, a total of **40 patients** will be studied. If the total number responding is less than or equal to 12, the drug is rejected.

For the AML Arm B:

**Note: As of July 2018, Arm B was closed after accruing 27 patients.**

The optimal two-stage design to test the null hypothesis that  $P \leq 0.200$  versus the alternative that  $P \geq 0.400$  has an expected sample size of 20.58 and a probability of early termination of 0.747. If the drug is actually not effective, there is a 0.050 probability of concluding that it is (the target for this value was 0.050). If the drug is actually effective, there is a 0.200 probability of concluding that it is not (the target for this value was 0.200). After testing the drug on 13 patients in the first stage, the trial will be terminated if 3 or fewer respond. If the trial goes on to the second stage, a total of **43 patients** will be studied. If the total number responding is less than or equal to 12, the drug is rejected.

For the pre treated Arm C:

**Note: As of October 2017, Arm C was closed after accruing 7 patients.**

The optimal two stage design to test the null hypothesis that  $P \leq 0.05$  versus the alternative that  $\geq 0.200$  has an expected samples size of 10 and a probability of early termination of 0.508. If the drug is actually not effective, there is a 0.050 probability of concluding that it is (the target for this value was 0.050). If the drug is actually effective, there is a 0.200 probability of concluding that it is not (the target of this value was 0.200). After testing the drug on 10 patients in the first stage, the trial will be terminated if zero patients respond. If the trial goes on the second stage, a total of **29 patients** will be studied. If the total number responding is less than or equal to 3, the drug is rejected.

### 7.2 Statistical Analysis

We will estimate the distribution of time to death, time to relapse, and time to progression by the Kaplan-Meier method. Baseline patient and disease characteristics will be summarized using descriptive statistics (e.g. mean, median, standard deviation, range, frequency and percentage), histograms and box plots.

The key PD variable is percentage change in S6 inhibition from baseline to post-treatment, defined as  $100 * ([\% \text{ S6-positive blasts post-treatment} - \% \text{ S6-positive blasts at baseline}] / \% \text{ S6-positive blasts at baseline})$ . We will examine distributional characteristics by: histograms, box plots and descriptive statistics (e.g., mean, median, standard deviation, range). Variability will be of particular interest. We will conduct within-patient comparison of baseline versus posts-treatment percentages by Student's paired *t* test. A nonparametric Wilcoxon signed ranks test will be employed if normality cannot be assumed or achieved by simple transformation. We will also investigate association of S6 response and clinical response. We will make box plots of the percentage change in S6 inhibition by complete response (e.g., CR/non-CR) category. Mean and standard deviation estimates will be of particular interest for the design of future hypothesis-testing studies. With the small number of subjects these analyses are likely to have only modest power, and we will not perform formal significance tests.

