In vitro activity of the combination of azacitidine and sirolimus has been preliminarily studied by one group from China. Sun et al tested the combination of drugs against single agent in two gastric cancer lines. MTT survival assays demonstrated additive effect on reduction of cell viability. Western blots demonstrated a marked increase in the upregulation of PTEN and p27 in cell lines treated with both drugs. Zhang et al demonstrated a similar additive effectiveness both in vitro colorectal cancer lines treated and in vivo with mouse models treated with the combination of azacitidine and sirolimus.

Recently, the preliminary results of a combination of azacitidine and MTOR inhibitors in AML have been presented at an international meeting. Wei et al studied the effect of the combination of azacitidine and everolimus on 37 relapsed and refractory AML patients. 32% had a clinical response with a median OS of 211 days and PFS of 178 days, demonstrating the potential for significant activity in this notably difficult population to treat.

[figure not shown]
We seek new strategies to lengthen survival in patients with high risk MDS, AML refractory to treatment or unable to tolerate ICT. We propose to add a novel agent, an mTOR inhibitor (MTI), sirolimus, to act synergistically with azacitidine to improve response rates. In addition, we note that the benefit of azacitidine is limited by acquired resistance and the addition of sirolimus may rescue or augment the response to those previously treated with azacitidine. This protocol details a phase II study to determine the efficacy of the combination of the two drugs in these settings.

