### **2.2 Secondary Objectives**

- To determine the pharmacodynamic effect of sirolimus on inhibition of mTOR signaling in adults with high-risk MDS, or relapsed or refractory AML or those unable or unwilling to tolerate high dose chemotherapy.
- To determine the safety and tolerability of sirolimus and azacitidine in adults with high-risk MDS, or relapsed or refractory AML or those unable or unwilling to tolerate high dose chemotherapy.
- To determine the progression free survival and overall survival in adults with high-risk MDS, or relapsed or refractory AML or those unable or unwilling to tolerate high dose chemotherapy
- To determine if the quality of life of patients is improved with the combination of azacitidine and sirolimus when compared to historical controls of azacitidine alone.

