  - At least 50% decrement from maximum remission/response in
    - granulocytes or platelets
    - Reduction in Hgb by 2 g/dL
    - Transfusion dependence
  - **Failure**
    - Death during treatment or disease progression characterized by worsening of cytopenias, increase in percentage of bone marrow blasts, or progression to more advanced MDS FAB subtype than pretreatment
  - **Relapse after CR or PR**
    - At least 1 of the following:
      - Return to pretreatment bone marrow blast percentage
      - Decrement of 50% from maximum remission/response levels in
        - granulocytes or platelets
      - Reduction in Hgb concentration by 1.5 g/dL or transfusion dependence

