### 3.2.1.1.2 Response Criteria - AML

- **Complete Remission (CR)**
  - Peripheral Blood Counts -Neutrophil count  $1 \times 10^9/L$ .
  - Platelet count  $\geq 100 \times 10^9/L$ .
  - Reduced hemoglobin concentration or hematocrit has no bearing on remission status.
  - Leukemic blasts must not be present in the peripheral blood.
  - Cellularity of bone marrow biopsy must be  $> 20\%$  with maturation of all cell lines with  $< 5\%$  blasts.
  - Extramedullary leukemia, such as CNS or soft tissue involvement, must not be present.
- **Complete Response in the absence of total platelet recovery (CRp)**
  - Bone marrow ( $<5\%$  blasts) with adequate bone marrow cellularity, no evidence of circulating blasts or extramedullary disease and normalization of peripheral blood counts except for platelets (neutrophil count  $=1,000/\mu L$ ).
- **Partial Remission (PR)**
  - Requires that all of the criteria for complete remission be satisfied except that the bone marrow may contain  $> 5\%$  blasts but  $< 25\%$  blasts. A marrow with  $<5\%$  blasts that contain Auer rods will also be considered a PR
- **Progressive Disease (PD)**
  - An increase of at least 25% in the absolute number of leukemic cells in peripheral blood or bone marrow/aspirate, the development of extramedullary disease, or other evidence of increased tumor burden.
- **Relapse**
  - Relapse following complete remission is defined as: Reappearance of blasts in the blood.
  - Presence of 5% blasts, not attributable to another cause (e.g., bone marrow regeneration).
  - If there are no circulating blasts and the bone marrow contains 5% to 20% blasts, then a repeat bone marrow performed 1 week later documenting more than 5% blasts is necessary to meet the criteria for relapse.

Patients achieving a CR, CRp, or PR will be considered responders. Given the lag between first administration of azacitidine and clinical response, bone marrow examinations will be performed before entry into study, at 6 months, and then at least 6-month intervals afterwards. The biopsies will help

document response to treatment for both MDS and AML patients and to determine endpoints where necessary. Best response will be used for study endpoint.

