## **6 Study Procedures**

At enrollment each subject will have a medical history taken, a physical exam (including neurological exam), vital signs, ECOG performance status, and laboratory studies including CBC with differential, liver function tests, electrolytes, uric acid, and glucose as well as a pregnancy test if applicable. An HSV titer is recommended. Patients who have not had a bone marrow biopsy sample within the last 4 weeks will require a bone marrow biopsy and aspirate.

Patients will be offered an option to complete the standard of care chemotherapy treatment at the following Jefferson Health network hospitals: Center City Hospital, Abington Hospital, Aria Hospital, Methodist Hospital and NJ Division (Kennedy) Hospital. All research related procedures are to be done at Jefferson Center City campus.

Patients will be followed for disease status and survival for 5 years following the enrollment of the last patient. These follow-ups will be via phone call, chart review, or in conjunction with their routine office visits every 3 months.

See Attachment #2 for Study Procedures Table.

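### Progression-free survival is a secondary objective, but section 7.2 neither estimates it nor says how deaths without progression or relapse are handled

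*Combined protocol and SAP*

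**What the plan says.** Section 2.2 lists among the secondary objectives: "To determine the progression free survival and overall survival in adults with high-risk MDS", and extends this to the AML populations. Section 7.2 gives one sentence on time-to-event analysis: "We will estimate the distribution of time to death, time to relapse, and time to progression by the Kaplan-Meier method". It states no time origin, event definition or censoring rule. The secondary endpoints in section 3.2.2 are safety, pharmacokinetics, pharmacodynamics and quality of life; neither PFS nor overall survival appears there.

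The event definitions sit in the response criteria. AML progression begins "An increase of at least 25% in the absolute number of leukemic cells in peripheral blood" and goes on to other signs of disease burden. For AML relapse the text is "Relapse following complete remission is defined as: Reappearance of blasts in the blood", followed by marrow criteria. MDS progression and relapse rest on blasts, blood counts and transfusion need. Death enters only the MDS Failure category: "Death during treatment or disease progression characterized by worsening of cytopenias". No time-to-event analysis refers to that category.

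On data collection, section 6 says: "Patients will be followed for disease status and survival for 5 years following the enrollment of the last patient". Contacts are every 3 months.

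**The concern.** PFS counts death from any cause as an event. Time to progression does not, unless the plan says so. Section 7.2 lists death separately from progression and relapse, and those two are defined by disease findings alone. An analyst following the text would most naturally treat a patient who dies without progression as censored. Kaplan-Meier then treats that patient as someone who could still progress later, although death has ruled this out.

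Two things follow. First, the quantity named in the objective is not produced. A reader who takes the time-to-progression median as PFS, for instance to set it beside the PFS in the azacitidine-everolimus study cited in section 1.1, would compare unlike quantities. Second, one minus Kaplan-Meier is too high as an estimate of the probability that progression or relapse occurs. These are errors against two different targets, so they do not add up to a single statement that disease control is overstated.

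**Working it through.** The plan gives no event count, precision or power for PFS, time to progression or relapse, so there is no figure of its own to reproduce. The check has three steps.

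**1. Objective against analysis.**

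| Quantity | Objective (2.2) | Analysis (7.2) | Is death an event? |
|---|---|---|---|
| Overall survival | yes | time to death | yes |
| PFS | yes | none | no definition given |
| Time to progression | no | Kaplan-Meier | not in the disease criteria |
| Time to relapse | no | Kaplan-Meier | not in the disease criteria |

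**2. Direction.** Suppose deaths without progression are censored. Patients leave the risk set at the same times in the PFS and time-to-progression analyses, but the latter counts fewer events. Its curve therefore lies on or above the PFS curve throughout, whatever the shape of the hazards. One minus that curve lies on or above the cumulative incidence of progression, because the latter does not let patients who have died progress later.

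**3. Size, as an illustration.** Section 1.1 cites "median OS of 211 days and PFS of 178 days" for azacitidine with everolimus in relapsed and refractory AML. Assume constant hazards and let f be the share of first events that are deaths without progression. The documents do not give f. The range of 8% to 50% is assumed. Its low end borrows the 8% toxic death rate in section 3.2.2.1, which is a proportion of patients and so only a rough guide to f.

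- Total hazard: h = ln 2 / 178 = 0.003894 per day.
- Kaplan-Meier median time to progression with deaths censored: ln 2 / [h(1 − f)] = 178 / (1 − f).
- One minus Kaplan-Meier at 6 months (182.6 days): 1 − exp[−h(1 − f) × 182.6].
- Cumulative incidence at 6 months: (1 − f) × [1 − exp(−h × 182.6)] = (1 − f) × 0.509.

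| Assumed f | Median time to progression (days) | Ratio to PFS of 178 | One minus Kaplan-Meier, 6 months | Cumulative incidence, 6 months |
|---|---|---|---|---|
| 8% | 178 / 0.92 = 194 | 1.09 | 48.0% | 46.8% |
| 30% | 178 / 0.70 = 254 | 1.43 | 39.2% | 35.6% |
| 50% | 178 / 0.50 = 356 | 2.00 | 29.9% | 25.4% |

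Simulations of 400,000 patients at 30% and 50% gave medians of 254 and 356 days, in line with the formula.

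**Limit of the illustration.** Section 1.1 gives a median survival of 21.1 months on azacitidine in high-risk MDS. Under constant hazards that is an all-cause death rate of ln 2 / 21.1 = 0.033 per month. The 30% row implies death without progression at 0.30 × 0.003894 × 30.44 = 0.036 per month, already above that total. The middle and upper rows therefore cannot be carried over to untreated high-risk MDS as they stand.

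**The case against.** The strongest reply is that this is a gap in definition. Section 7.2 says nothing about censoring, so deaths might be meant as events, and the MDS Failure category does group death during treatment with progression. This stands in part. A reader might infer that the plan instructs the analyst to censor deaths; it does not, and censoring is an inference from the event definitions. But if deaths were meant to count, the text would still have to say so, and the Failure category is limited to MDS and to death during treatment.

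A reader might also infer that many patients will die before progression can be seen, since "bone marrow examinations will be performed before entry into study, at 6 months, and then at least 6-month intervals afterwards". The documents do not show this. Progression can be documented from blood findings in both diseases. Attachment 2 schedules laboratory tests twice weekly on treatment and weekly off treatment in cycles 1 to 6, and allows marrows more often at the investigator's discretion.

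Nor does high early mortality describe the whole trial. It fits the cited survival in AML (7 to 9 months) and after decitabine failure (under 5 months) better than untreated high-risk MDS. Arm A is the only arm still open and is planned at 40 of 74 patients. It now also admits pretreated MDS, however, and the 27 patients in Arm B and 7 in Arm C still need analysis.

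Finally, the arms are judged on response rate by two-stage designs, and PFS could be derived from data already collected. Both points stand. They limit the consequence but do not close the gap.

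**Conclusion.** The point holds in a limited form. It is certain from the text that PFS is an objective with no definition and no matching analysis, while overall survival is covered. It is likely, though not stated, that deaths without progression or relapse would be censored. If they are, the direction is certain: time to progression exceeds PFS, and one minus Kaplan-Meier exceeds cumulative incidence.

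The size is not known. Relative to a PFS median of 178 days, the excess runs from about 9% to 100% for assumed shares of 8% to 50%, under constant hazards and with a relapsed or refractory AML reference. It is probably smaller in untreated high-risk MDS. This should be corrected, but it concerns a secondary objective and leaves the primary response test untouched.

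**What to change.** In section 7.2, add PFS as the analysis of the section 2.2 objective. Define it as the time from a stated origin to the first of progression, relapse or death from any cause, give a censoring rule for patients without an event, and estimate it by Kaplan-Meier. Keep time to death for overall survival.

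If time to progression and time to relapse are also wanted, keep them as separate descriptive quantities, with relapse assessed among responders. Estimate both by cumulative incidence, with death without the event as a competing event.

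The cost is a few sentences and a little more analysis. Disease status and survival are already collected every 3 months, so no new data are needed. The reported times will look less favourable than time-to-progression medians with deaths censored.

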We, along with the University of Pennsylvania have completed a phase I trial and 2 follow up trials of sirolimus with mitoxantrone, etoposide, and cytarabine in relapsed, refractory, or secondary AML. The maximum tolerated dose (MTD) was found to be a 12mg loading dose and 4mg daily dose. 27 patients were treated at this dose. Grade 3 or higher toxicities seen in patients treated at or below the MTD were neutropenic fevers in all patients, documented infections in 15 subjects, transient liver function abnormalities in three subjects, non-infectious diarrhea in two subjects, mucositis in two subjects, and transient metabolic abnormalities (hyperglycemia, hypocalcemia, hyperkalemia, hypernatremia), transient cerebellar ataxia, or thrombosis all in one subject each. We recently reported data from a phase I/II trial of the combination of sirolimus and MEC in relapsed/refractory AML that correlated response to combination therapy with baseline mTOR activation. Patients whose leukemic blasts at baseline had constitutive S6 phosphorylation and who experienced a greater than 50% reduction in the number of blast with pS6 had an impressive 67% response rate, while only 33% of those non-phosphorylated at baseline or rapamycin non-responders had a clinical response.

Our group completed a pilot trial in ALL patients combining sirolimus at the same doses with hyperCVAD and no safety issues were encountered. We have completed enrollment on a phase II trial of sirolimus MEC at Jefferson and the University of Pennsylvania and again, no safety concerns were seen therefore we believe combining this dose of sirolimus with azacitidine will not lead to unexpected toxicities.

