#### 3.2.2.3 Pharmacodynamic assessment

The secondary pharmacodynamic endpoint is to determine if rapamycin effectively inhibits mTOR signaling at levels achieved in this regimen.

We want to define in vivo, the percentage of baseline samples that have activation of the S6 ribosomal protein and the percentage of those that were found to be activated which are subsequently inhibited by sirolimus in the post treatment sample. [S6 positive blasts post-treatment minus % S6 positive blasts at baseline]

We will determine the ability of oral sirolimus to inhibit mTOR in leukemic blasts. This will be measured by intracellular flow cytometry for phosphorylation of the downstream signaling target S6 ribosomal protein as a surrogate for mTOR activity. Flow results will be confirmed by Western blot as appropriate. The in vivo effects of sirolimus will be compared to a whole blood *ex vivo* rapamycin dose response curve for each sample as well as to sirolimus levels obtained at the time of pharmacodynamic measurements. Finally, S6 inhibition will be correlated with clinical outcome. We will draw PD datapoints on day 1 before treatment, Day 4 before azacitidine administration. If patient have less than 5000/ $\mu$ l of blasts in the periphery, than a bone marrow aspirate will be performed for analysis.

We hypothesize that oral sirolimus will fully inhibit S6 in sampled leukemic blasts if concentrations exceed a threshold established by *ex-vivo* rapamycin therapy of the baseline sample. We will therefore expose this sample to increasing doses of rapamycin *ex vivo* and then measure mTOR activation by flow cytometry.

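### The key PD variable divides by baseline S6 positivity with no rule for non-activated samples, so its mean and SD are unstable

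*Combined protocol and SAP*

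**What the plan says.** Section 7.2 declares one main pharmacodynamic quantity: "The key PD variable is percentage change in S6 inhibition from baseline to post-treatment". Its formula is 100 × (post − baseline) / baseline, where both terms are percentages of S6-positive blasts and the denominator is the percentage of "S6-positive blasts at baseline". Section 7.2 then plans histograms, box plots, mean, median, SD and range. It plans a paired comparison of the two percentages (t test, or Wilcoxon if normality fails), and a box plot of the relative change "by complete response (e.g., CR/non-CR) category". It names the mean and SD as the estimates of interest for designing later studies. It states no PD analysis set and no rule for a zero or low baseline.

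Section 3.2.2.3 asks two different things. The first is what share of patients' samples show S6 activation before treatment. The second looks only within that activated group: "the percentage of those that were found to be activated which are subsequently inhibited by sirolimus in the post treatment sample". Beside these it prints, in brackets, an undivided expression: "S6 positive blasts post-treatment minus % S6 positive blasts at baseline".

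Section 1.4 reports from the earlier sirolimus-MEC trial that "only 33% of those non-phosphorylated at baseline or rapamycin non-responders had a clinical response". Section 6.1.1 describes the positive and negative gates used to score blasts, but sets no minimum positivity for calling a sample activated.

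**The concern.** A relative change needs a denominator safely away from zero. By making baseline activation an outcome, Section 3.2.2.3 accepts that some samples will not be activated, and Section 1.4 confirms that such patients existed in the earlier trial. For them the Section 7.2 ratio is either undefined or driven by small fluctuations in a small number.

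The scale is also lopsided: the value cannot fall below -100% but has no upper limit. A few low-baseline samples can therefore pull the mean upward and inflate the SD. These are the two figures that Section 7.2 intends to hand to later study designs. A diluted mean with an inflated SD would understate the pharmacodynamic effect and overstate its variability in any sample size built on them.

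Sections 3.2.2.3 and 7.2 are also not reconciled. One asks about inhibition among activated samples and shows a plain difference; the other analyses a ratio and never brings the activated-and-inhibited proportion into the analysis.

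**Working it through.** The plan gives no SD, effect size or sample size for the PD variable, so there is no figure to reproduce. The largest possible PD sample is 40 (Arm A) + 27 (Arm B) + 7 (Arm C) = 74, which matches the stated number of subjects.

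**1. Undefined values.** P(at least one zero baseline) = 1 − (1 − q)^n, where q is the assumed share of patients scoring exactly 0%.

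| q (assumed) | n = 40 | n = 74 |
|---|---|---|
| 1% | 33.1% | 52.5% |
| 5% | 87.1% | 97.8% |
| 20% | >99.9% | >99.9% |

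**2. Effect on the mean and SD.** Take four invented patients, baseline to Day 4: 60→20, 50→20, 40→15, 2→8.
- Relative changes: -66.7, -60.0, -62.5, +300.0. Mean +27.7%, median -61.3%, SD 181.5.
- Absolute changes: -40, -30, -25, +6. Mean -22.25 points.
- First three patients only: mean relative change -63.1%, SD 3.4.

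The example was chosen to show the mechanism. With 2→2 in place of 2→8, the mean is (-66.7 − 60.0 − 62.5 + 0)/4 = -47.3%: diluted but not reversed. The sign flips only when the fourth patient rises by more than 66.7 + 60.0 + 62.5 = 189.2%, that is from 2 to above about 5.8.

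**3. Threshold for a sign change.** Let a share f of patients have low baselines and let the rest fall by 70%. The mean is zero when the low group averages +70 × (1 − f)/f.
- f = 20%: 70 × 0.8/0.2 = +280% (1% to 3.8%, or 2% to 7.6%).
- f = 10%: 70 × 0.9/0.1 = +630% (1% to 7.3%).

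If the low group simply does not change, the mean with f = 20% is 0.8 × (-70) = -56%.

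**4. How often.** Simulation, 3,000 runs per row, n = 40. Assumed: 20% of patients at a true 2% positivity with no drug effect, and the rest well above zero with the stated true reduction. Extra noise means beta-binomial sample-to-sample variation (concentration 30). Undefined values are left out of the mean.

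| True reduction | Blasts | Extra noise | Average of the mean relative change | Runs with mean above 0 | Mean if baseline ≥10% |
|---|---|---|---|---|---|
| 70% | 200 | no | -49.7% | 0% | -69.8% |
| 70% | 200 | yes | -48.7% | 3.9% | -68.6% |
| 70% | 1,000 | yes | -5.0% | 32.1% | -68.7% |
| 50% | 200 | no | -33.7% | 0.3% | -49.7% |
| 50% | 200 | yes | -31.4% | 8.1% | -47.7% |
| 30% | 200 | no | -17.5% | 5.1% | -29.5% |
| 30% | 200 | yes | -12.8% | 20.4% | -26.7% |

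The median relative change and the mean absolute change had the wrong sign in 0% of runs in every row. Counting more blasts makes the ratio worse here, because very small baselines then register as tiny denominators instead of as zeros that drop out. The 10% floor is illustrative.

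**The case against.** Several stronger readings are tempting, and the documents do not support them.

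- **The two sections contradict each other.** A reader might infer two rival key variables. Section 3.2.2.3 gives only a bracketed fragment that matches the numerator of the Section 7.2 formula, and it never calls that fragment a variable or a summary. Only Section 7.2 names a key variable. What stands is that the two are not reconciled.
- **The mean will show the wrong sign.** This rests on invented data and assay noise that the documents do not give. With a 70% reduction and counting noise alone it never happened; dilution toward zero is the more usual result.
- **Many baselines will be zero.** Section 1.4 gives no percentage for its non-phosphorylated group and pools it with rapamycin non-responders. Section 1.5 reports that all five pilot baselines were S6-positive. Those were relapsed or refractory AML patients, so they say little about MDS, which is Arm A and the only arm still open.
- **Zero-baseline patients vanish from the report.** Section 3.2.2.3 counts the share of samples activated, so non-activated patients still appear there. The plan does not say what becomes of them in the Section 7.2 variable.
- **The primary endpoint is left out of the association.** The CR/non-CR split is introduced as an example, and Section 7.2 also plans a broader look at S6 response and clinical response. It remains true that the only display named is not split by the responder rule, "Patients achieving a CR, CRp, or PR will be considered responders".

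The strongest point on the other side is that robust summaries are already planned: the median, range and box plots, the paired comparison on raw percentages, and the fluorescence-intensity comparison in Section 6.1.1. This stands and limits the harm. It does not repair the mean and SD that Section 7.2 selects for future use.

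**Conclusion.** The concern holds for the mean and SD of the relative change. As written, the formula has no value at a zero baseline and is unstable near zero, and the protocol itself expects non-activated samples. Dilution is the likelier consequence: about -50% where the true reduction in activated patients is 70%, if 20% of patients sit at 2% positivity. A reversed sign is possible but needs a weak true effect or substantial noise at low baselines (0% to 32% of runs across the settings tried).

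All baseline distributions, noise levels and blast counts here are assumptions. The 20% share is taken as an upper value from the statement in Section 1.3 that the pathway is activated in at least 80%; the sentence can be read as referring to patients or to cells.

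The analysis is secondary and descriptive, and no Simon decision depends on it. It should be corrected, but it does not threaten the trial's primary conclusion.

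**What to change.** In Section 7.2, with matching wording in Section 3.2.2.3:

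1. Report the mean and SD of the relative change only for samples activated at baseline, with the activation threshold fixed beforehand from the gates in Section 6.1.1.
2. Report the absolute difference in percentage of S6-positive blasts for all patients with an evaluable pair.
3. Lead with the median.
4. Report the Section 3.2.2.3 proportion: activated samples that are inhibited, over all activated samples, with the inhibition cut-off fixed beforehand. The greater-than-50% reduction in Section 1.4 refers to the number of blasts with pS6, so it does not carry over to a percentage-positive scale without a stated justification.
5. Beside CR/non-CR, plot by the responder definition within each disease: CR, CRp or PR for AML. The MDS criteria have no CRp and add marrow CR and hematologic improvement, so state which MDS categories count as response.

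The cost is a few lines of text, with no new samples. The relative-change summary will cover fewer patients. The absolute difference has its own limit: a sample at 2% can fall by at most 2 points, so its mean depends on the mix of baselines and should be read beside the baseline distribution.
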